**Table 3 Criteria for Best overall confirmation with RECIST 1.1**

Overall response at previous time point	Overall response at current time-point	Best Overall Response
CR	CR	CR
CR/PR	PD	SD
PR	CR	PR
PR	PR	PR
SD	Any	SD

Non-evaluable subjects for BOR will be summarized by reason.

**Table 4 BOR of NE reasons**

BOR of non-evaluable reasons	BOR
No baseline tumor assessment	NE
No post baseline assessment	NE
All post baseline tumor Assessments have overall response NE.	NE
First tumor assessment with overall response as PD reported after 2 or more missing or NE on treatment tumor assessment (16 weeks or more from the first dose of treatment administered.)	NE

Note:

- Best response could be confirmed during the follow up period.
- Clinical progression /deterioration will not be considered as documented disease progression.

#### 4.4.1.2 iRECIST Best Overall Response (iBOR)

The Best Overall Response according to iRECIST (iBOR) is the best response recorded from the start of the study treatment until the end of treatment, taking into account any requirement for confirmation.

iUPD will not override a subsequent Best Overall Response of iSD, iPR, or iCR, meaning that iPR or iSD can be assigned, providing that the criteria for iCPD are not met.

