4.3.2 Modified RECIST 1.1 for Immune-based Therapeutics

Accumulating evidence indicates that patients with solid tumors treated with immunotherapy may derive clinical benefit despite initial evidence of PD. For the purpose of establishing the Phase 2 secondary endpoint the iRECIST (modified RECIST 1.1 for immune-based therapeutics [22]) will be used to assess tumor response for all treated subjects.

Subjects with RECIST 1.1-defined PD (iUPD [iRECIST]) should have a repeated tumor assessment 4-8 weeks later in order to confirm PD and will be permitted to continue treatment as long as they meet the criteria in [Section 3.2.6.2](#) and they do not have confirmed PD as defined by iRECIST. Subjects that are deemed clinically unstable are not required to have repeat imaging for confirmation of PD.

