#### 3.1 Efficacy population

Subjects evaluable for efficacy (tumor response) are defined as those who have measurable disease and at least one evaluable (post-baseline) tumor assessment performed during the treatment period or within 30 days after the administration of the last dose of treatment.

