### 4.4.1 Best Overall Response

#### 4.4.1.1 RECIST confirmed Best Overall Response (BOR)

The confirmed Best Overall Response (BOR) is defined as the best response presented according to RECIST v1.1 from the inclusion in the study to documented disease progression. (Only tumor assessments performed before the end of treatment visit date or within 30 days after the administration of the last dose of treatment will be considered in the assessment of BOR).

Partial and complete responses should be confirmed.

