##### 4.4.2.2 iRECIST Overall Response Rate (iORR) - Secondary Objective

The immune Overall Response Rate (iORR) is defined as the proportion of subjects who show as Best Overall Response by iRECIST an immune confirmed Complete Response (iCR) or immune confirmed Partial Response (iPR).

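### The iRECIST best response stops at end of treatment while RECIST best response and the analysis population run to 30 days after last dose, so iORR can fall below ORR on the same scans

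*SAP*

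**What the plan says.** Four parts of the SAP bear on this.

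- **RECIST BOR (4.4.1.1)** limits the scans that count: "Only tumor assessments performed before the end of treatment visit date or within 30 days after the administration of the last dose of treatment".
- **The note under Table 4**, in the same RECIST section, adds: "Best response could be confirmed during the follow up period".
- **iBOR (4.4.1.2)** "is the best response recorded from the start of the study treatment until the end of treatment", with a closing clause that confirmation requirements are to be respected. It has no 30-day extension and does not say where a confirming scan may fall.
- **The Efficacy population (3.1)** accepts a post-baseline scan "performed during the treatment period or within 30 days after the administration of the last dose of treatment". Table 1 assigns both ORR and iORR to this population.

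iORR (4.4.2.2) is the "proportion of subjects who show as Best Overall Response by iRECIST an immune confirmed Complete Response (iCR) or immune confirmed Partial Response (iPR"), so it inherits the iBOR window. Protocol 6.3 sets no window for either rate. SAP 2.4, which lists departures from the protocol, neither mentions nor justifies a shorter window for iRECIST.

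**The concern.** The two response rates are meant to differ only in how progression is handled: iRECIST lets a response count after an unconfirmed progression. On the same scans, iORR should then equal or exceed ORR. With a shorter scan window for iBOR, iORR can instead come out lower, and a reader of the report would have no way to tell from the two rates that the window was the cause.

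The same window carries into iDCR (SAP 4.4.3.2). It also carries into the iRECIST DoR planned in SAP 5.3.2.2, to the extent that DoR is restricted to confirmed responders. In addition, a subject whose only post-baseline scan falls between the end-of-treatment date and day 30 after last dose is in the Efficacy population and has a RECIST BOR, but has no scan that can supply an iBOR. A single scan cannot give a confirmed response, so that subject bears on iDCR and the iBOR table rather than on iORR.

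**Working it through.** **Inputs**
- Confirmation interval for CR or PR: 4 weeks = 28 days (Protocol 4.3).
- End of treatment: the date on the End of Treatment form, which SAP 4.1 uses to close the on-treatment period. SAP 4.4.1.2 does not cite it, so its use here is an inference. Its distance from last dose is not given.
- Cohort sizes and planning rates: 2/11 in Cohorts 1 and 2, 3/18 in Cohort 3 (SAP 5.1).
- Intervals: exact two-sided 90% (SAP 5.3.2.1 and 5.3.2.2).

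**Step 1. The plan's own figures.** SE = √(p(1−p)/n).
- √((2/11)(9/11)/11) = 11.63%; stated 11.6%.
- √((3/18)(15/18)/18) = 8.78%; stated 8.8%.

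Both reproduce.

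**Step 2. Where the windows part.** Call the period after the end-of-treatment date, but within 30 days of last dose, the gap. There are three kinds of responder:
- **A:** response first seen on treatment, confirmed in the gap. Example: last dose and PR at week 8, form dated week 10, PR again at week 12. The confirming scan is (12−8)×7 = 28 days after last dose, inside the RECIST window without help from the Table 4 note.
- **B:** response first seen in the gap, confirmed 28 days or more later. The confirming scan is itself within 30 days only if the first was seen no later than 30−28 = 2 days after last dose. Otherwise B needs the Table 4 note to count for ORR.
- **C:** response first seen on treatment, confirmed in follow-up more than 30 days after last dose and after the end-of-treatment visit.

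Two points of the text are open: whether the Table 4 note lifts the 30-day limit for a confirming scan, and whether the confirmation clause in 4.4.1.2 lets an iRECIST confirming scan fall after end of treatment.

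| Note lifts the RECIST limit? | iRECIST confirmation may come later? | A counts for | B counts for | C counts for |
|---|---|---|---|---|
| No | No | ORR only | neither* | neither |
| Yes | No | ORR only | ORR only | ORR only |
| Yes | Yes | both | ORR only | both |
| No | Yes | both | neither* | iORR only |

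*Apart from the 2-day exception, where B counts for ORR only.

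In three of the four readings the window alone can push iORR below ORR. In the fourth, apart from that exception, the mismatch runs the other way. No reading gives the two rates the same scans.

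**Step 3. Size of one affected subject, at the planning rates.**

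| Cohort | ORR (90% CI) | iORR with one responder lost (90% CI) | Difference |
|---|---|---|---|
| 1 or 2 | 2/11 = 18.2% (3.3–47.0) | 1/11 = 9.1% (0.5–36.4) | 9.1 points |
| 3 | 3/18 = 16.7% (4.7–37.7) | 2/18 = 11.1% (2.0–31.0) | 5.6 points |

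**Step 4. How often.** The documents give no figure. As an assumption, let q be the share of RECIST responders who count for ORR but are lost to iORR. The chance of losing at least one of k responders is 1−(1−q)^k.

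| q | k = 2 | k = 3 |
|---|---|---|
| 5% | 9.8% | 14.3% |
| 10% | 19.0% | 27.1% |
| 20% | 36.0% | 48.8% |
| 30% | 51.0% | 65.7% |

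This ignores iRECIST responses gained after an unconfirmed progression, which would offset the loss.

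**The case against.** The strongest case against is that this is a wording gap with little practical effect.

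- **Confirmation is not excluded for iRECIST.** The clause in 4.4.1.2 may allow a later confirming scan, and the Table 4 note is not worded as RECIST-only, although it sits in the RECIST section. This stands: the confirmation part is an ambiguity. A reader might infer that any iRECIST confirmation after treatment is barred, but the SAP does not say so.
- **A later example would prove less.** A reader might take PR at week 8, treatment stopped at week 10 and PR again at week 16 as a clear ORR-only responder. That scan is (16−10)×7 = 42 days after stopping, so it counts for ORR only if the Table 4 note overrides the 30-day limit. The week-12 example does not depend on this.
- **Few scans can fall in the gap.** Scans are scheduled during treatment (Protocol 4.3). The end-of-treatment scan is only for subjects who stop before their first assessment (Protocol 4.1.2.8), and follow-up lists none (Protocol 4.1.3, Appendix A). If the end-of-treatment date falls about 30 days after last dose, the gap closes. This limits frequency, but it does not remove the mismatch: Protocol 4.3 asks for confirming scans without restricting them to the treatment period, and the SAP's DoR and PFS censoring rules anticipate assessments in follow-up.
- **The late responses iRECIST is meant to capture are not shown to be lost.** A reader might infer that they are. But the subject with a first progression "should have a repeated tumor assessment 4-8 weeks later in order to confirm PD" (Protocol 4.3.2) and may stay on treatment meanwhile, so a response on that scan would usually lie inside the iBOR window. If treatment stopped at the first progression, a scan 28 to 56 days later would mostly miss a 30-day window too.
- **No comparison of ORR with iORR is planned.** The study is exploratory, iORR is descriptive, and by-subject listings of both assessments will be produced (SAP 5.3.2.2). This stands, and it keeps the point modest.

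**Conclusion.** The mismatch holds on the text. iBOR ends at end of treatment, while RECIST BOR and the population that forms the iORR denominator extend to 30 days after last dose, and no reason is given. A response confirmed in between, on the literal text, or first seen in between if follow-up confirmation is accepted for RECIST, counts for ORR and not for iORR. Each such subject costs 9.1 points of iORR in a cohort of 11 and 5.6 points in a cohort of 18.

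This rests on reading end of treatment as the form date and on that date falling less than 30 days after last dose. The number affected is unknown and probably small. The primary ORR is not changed by the iBOR window. The documents do not support saying that iRECIST confirmation in follow-up is forbidden, or that a planned comparison of the criteria is invalidated. The change should still be made, because two programmers following this text could derive different iORRs.

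**What to change.** 1. In SAP 4.4.1.1, reconcile the 30-day limit with the note under Table 4. State that the initial response must fall in the assessment window, and state whether its confirming scan may fall later in follow-up. Do this first; otherwise the conflict is copied into iBOR.
2. In SAP 4.4.1.2, give iBOR the RECIST assessment window ("before the end of treatment visit date or within 30 days after the administration of the last dose of treatment") and the same explicit confirmation rule, so that the two rates differ only in how progression is handled.
3. Say which date is meant by end of treatment in both sections.
4. If a shorter iRECIST window is intended, say so and justify it in SAP 2.4.

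The cost is a few sentences in the SAP and a matching change to the derivation. No new scans or data are needed, and the sample size and stated standard errors do not change.

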#### 4.4.2 Overall Response Rate

##### 4.4.2.1 RECIST Overall Response Rate (ORR) - Primary Objective

The confirmed Overall Response Rate (ORR) is defined as the proportion of subjects having reached a confirmed Complete Response (CR) or Partial Response (PR) by RECIST 1.1, relative to the number of subjects belonging to the analysis population set.

##### 4.4.2.2 iRECIST Overall Response Rate (iORR) - Secondary Objective

The immune Overall Response Rate (iORR) is defined as the proportion of subjects who show as Best Overall Response by iRECIST an immune confirmed Complete Response (iCR) or immune confirmed Partial Response (iPR).

#### 4.4.3 Disease Control Rate

##### 4.4.3.1 RECIST Disease Control Rate (DCR)

The confirmed Disease Control Rate (DCR) is defined as the proportion of subjects having reached a confirmed Complete Response (CR), Partial Response (PR), or Stable Disease (SD) by RECIST 1.1, relative to the number of subjects belonging to the analysis population set.

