4.1.2.8 End of Treatment Visit

- Perform physical examination (including weight and vital signs)
- ECOG performance status
- Laboratory evaluations:
 - 1) Serum chemistry
 - 2) Hematology
 - 3) Coagulation
 - 4) Pregnancy test (if applicable)
- ADA serum sample
- Whole blood and plasma
- Cytokines plasma sample
- Record AEs and ConMeds
- Tumor assessment (for subjects that discontinue treatment before the first scheduled on study tumor assessment)

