4.3 Efficacy Assessments

Tumor assessment will be performed within 21 days prior to start of investigational therapy and during the Treatment Period (every 8 ± 1 week). Subject that discontinue treatment before the first scheduled on study tumor assessment (8 weeks following the first dose of APX005M) should have the tumor response evaluated at the end of treatment visit. Tumor assessments will follow RECIST 1.1 guidelines. Complete or partial responses should be confirmed at a subsequent time point 4 weeks later.

Subjects enrolled in Cohort 3 are required to have a minimum of 3 measurable target lesions. The lesions which are the first and second radiation therapy targets should be recorded.

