##### 4.4.3.2 iRECIST Disease Control Rate (iDCR)

The immune Disease Control Rate (iDCR) is defined as the proportion of subjects who show as Best Overall Response by iRECIST an immune confirmed Complete Response (iCR), immune confirmed Partial Response (iPR), or immune SD (iSD).

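### Disease control rate counts stable disease with no minimum time from first dose, so an early-stop scan showing unchanged tumors counts as disease control

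*SAP*

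**What the plan says.** **Definition of disease control.** SAP 4.4.3.1 counts confirmed CR, PR or "Stable Disease (SD) by RECIST 1.1, relative to the number of subjects belonging to the analysis population set". SAP 4.4.3.2 builds iDCR in parallel, from iCR, "immune confirmed Partial Response (iPR), or immune SD (iSD". Neither states how long after first dose the stable result must be seen.

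**Which scans count.** For RECIST BOR, SAP 4.4.1.1 uses "Only tumor assessments performed before the end of treatment visit date or within 30 days after the administration of the last dose of treatment". That closes the window at the late end only. For iBOR, SAP 4.4.1.2 runs from start to end of treatment, again with no earliest date.

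**How BOR is assigned.** SAP Table 3, "Criteria for Best overall confirmation with RECIST 1.1", pairs a previous with a current time point. An SD followed by anything gives SD, and no row carries a time condition. SAP Table 4 lists four NE reasons, among them "All post baseline tumor Assessments have overall response NE". An SD scan taken too early is not one of them.

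**Who is analysed.** SAP 3.1 admits a subject with measurable disease and one evaluable post-baseline scan, taken on treatment or within 30 days of the last dose. Its note keeps subjects who ended treatment for death or unconfirmed clinical progression before the first scheduled scan, and treats their response as NE.

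**When scans happen.** Protocol 4.3 schedules them "during the Treatment Period (every 8 ± 1 week". Subjects who stop before the first one "should have the tumor response evaluated at the end of treatment visit". Protocol 4.1.2.8 repeats this: "Tumor assessment (for subjects that discontinue treatment before the first scheduled on study tumor assessment".

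**Status of DCR.** SAP 2.4 says DCR is not in the protocol and was added in the SAP. SAP 5.3.4.2 also tabulates it by pre-treatment LDH, overall and by cohort.

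**The concern.** A tumor that has not changed two or three weeks after one dose says little about whether the drug controls disease. Most measurable lesions will not meet progression criteria in so short a time, whatever the treatment does. If such a scan counts as SD, a subject who left treatment before the planned assessment is scored as a success.

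The SAP already handles neighbouring cases with more care:

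- It uses the first scheduled scan as a boundary for early death and unconfirmed clinical progression, and sets those to NE. An early stop for toxicity with a week 3 scan showing SD goes the other way.
- Table 4 has a timing rule for a late first PD, but none for an early SD.
- Under SAP 4.4.5.1 an event-free subject who stops early is censored for PFS at that early scan and contributes almost nothing, yet is a full success in DCR.

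At stake is the meaning of DCR and iDCR, including DCR in the LDH subgroups, where denominators are smaller and each subject weighs more.

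**Working it through.** **Inputs.** Planned sizes are 11, 11 and 18 (SAP 5.1), total 40. The scan schedule is 8 ± 1 weeks (Protocol 4.3). The BOR window extends to 30 days after the last dose (SAP 4.4.1.1). The exact 90% Clopper-Pearson interval is stated for ORR (SAP 5.3.2.1) and is assumed here for DCR. The documents give no expected DCR and no count of early SD scans.

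**1. The plan's own figures.** The only design figures are the standard errors of the response rate, √(p(1 − p)/n):

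- 2/11: √(0.1818 × 0.8182 / 11) = 11.63%, stated as 11.6%.
- 3/18: √(0.1667 × 0.8333 / 18) = 8.78%, stated as 8.8%.

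Both reproduce. There is no DCR figure to reproduce.

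**2. Timing of the route.** The earliest scheduled scan is at 8 − 1 = 7 weeks, or 49 days after first dose. A subject who stops after one dose can have a scan counted up to 30 days after that dose (study day 31 in the SAP's numbering). An eligible scan can therefore fall well before the first scheduled one.

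**3. Following one subject through the rules.** Take one dose, a stop for toxicity, and an end-of-treatment scan at week 3 with unchanged tumors.

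- Efficacy population (SAP 3.1): included, with one evaluable post-baseline scan.
- NE note in SAP 3.1: does not apply, because the reason is neither death nor clinical progression.
- BOR window (SAP 4.4.1.1): the scan is inside it.
- Table 4: none of the four NE reasons applies.
- Result: the only recorded response is SD, nothing removes it, and DCR counts it.

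**4. Direction.** Let D be the number with disease control and k the number whose only basis is an early SD scan. The present rule gives D/n. With a minimum time and the subjects kept in the denominator, it is (D − k)/n, lower by k/n. If they also left the denominator, it would be (D − k)/(n − k), which cannot exceed D/n because D ≤ n. The present rule is therefore never lower.

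**5. Size per subject (k = 1).** 1/11 = 9.1 points, 1/18 = 5.6 points, and 1/40 = 2.5 points overall.

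**6. Illustration.** The starting counts are assumptions.

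| Cohort size | As written (90% CI) | One subject to NE, kept in denominator (90% CI) | Two subjects to NE, kept (90% CI) | One subject dropped from denominator |
|---|---|---|---|---|
| 11 | 5/11 = 45.5% (20.0–72.9) | 4/11 = 36.4% (13.5–65.0) | 3/11 = 27.3% (7.9–56.4) | 4/10 = 40.0% |
| 18 | 8/18 = 44.4% (24.4–65.9) | 7/18 = 38.9% (19.9–60.8) | 6/18 = 33.3% (15.6–55.4) | 7/17 = 41.2% |

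The intervals are wide and overlap heavily. The shift is small against sampling error, but it runs in one direction only.

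**The case against.** **DCR carries little weight.** It is a descriptive SAP addition in an exploratory study, with no target, test or decision rule. Swimmer plots and by-subject listings would show short SD to a careful reader. This stands as to importance, but those displays do not change the DCR figure. The planned duration of stable disease (SAP 2.2.3.2) is not defined, so it does not close the gap either.

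**The reference to RECIST 1.1, or the word confirmed, may supply the rule.** Neither document writes an SD interval, and what an analyst would take from the cited criteria cannot be checked here. Table 3 requires no confirmation of SD. A reproducible rule has to be stated.

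**Stronger readings that a reader might infer.**

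- *Table 3 itself orders SD for a single early scan.* It does not: it pairs two time points, and a lone scan is outside its literal reach. The problem is silence, in the missing lower time limit and in Table 4.
- *Every early stop becomes a success.* The note in SAP 3.1 makes death and unconfirmed clinical progression NE. The route mainly concerns toxicity, withdrawal and similar reasons.
- *The CR/PR-then-PD row of Table 3 has the same fault.* That row needs two scans, and on the 8 ± 1 week schedule the first normally falls at week 7 or later. Almost nothing is affected.
- *iDCR is distorted in the LDH subgroup.* SAP 5.3.4.2 names DCR only.

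**Conclusion.** The point holds as a gap in the definition. As written, SD or iSD at any time after first dose counts as disease control, and the protocol's early-stop scan gives a real route for it. The bias, if any, is upward.

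The size is 9.1 points per such subject in Cohort 1 or 2 and 5.6 points in Cohort 3. These figures use planned enrolment. The actual denominators are the analysis populations and may differ, partly because SAP 2.3.5 records that replacement of subjects was stopped. The number of such subjects is not given, so a large total inflation (for example 3/11 = 27.3 points) is not supported. The total could also be zero.

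DCR is affected by cohort, overall and in the LDH subgroup. iDCR shares the definitional gap, although SAP 4.4.1.2 does not say whether a scan at the end-of-treatment visit falls inside its window. A reader might infer that the primary result is at risk. It is not: ORR counts only confirmed CR and PR, so reclassifying SD leaves it unchanged.

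**What to change.** In SAP 4.4.1 and 4.4.3:

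- Count SD or iSD only if documented at least 7 weeks (49 days) after first dose. This is the lower edge of the protocol's own 8 ± 1 week window. It is a choice drawn from that schedule, not a rule already in the documents.
- Class earlier SD-only results as NE, and add that reason to Table 4.
- Keep these subjects in the DCR and iDCR denominators.
- State that the NE note in SAP 3.1 prevails if a subject who stopped early for death or unconfirmed clinical progression also has an SD scan. Table 4 does not list that case.

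The cost is a short SAP amendment, one table row and one date check in the program. DCR may come out somewhat lower; ORR does not change. Making the change before database lock avoids a later choice about who counts as controlled.

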##### 4.4.3.2 iRECIST Disease Control Rate (iDCR)

The immune Disease Control Rate (iDCR) is defined as the proportion of subjects who show as Best Overall Response by iRECIST an immune confirmed Complete Response (iCR), immune confirmed Partial Response (iPR), or immune SD (iSD).

